5.2 Randomization

Sixty patients will be recruited according to the sample size calculation. Randomization will be performed by a Research Patient Coordinator and the patient assigned to the Thunderbeat™ group or the conventional group in a 1:1 ratio. Randomization will only occur after the patient has signed the informed consent and will be documented in the case report file as well as communicated to the treating surgeon.

Thunderbeat™ group (n=30)

In the Thunderbeat™ group, dissection and hemostasis of vessels will be performed using the Thunderbeat™ device (Olympus, Japan).

Control group (n=30)

In the conventional group, scissors, ligatures, clips and sutures will be used for dissection and hemostasis as necessary.

Minimizing treatment bias

A standardized operation technique will be used in both groups. The same Thunderbeat™ device will be used throughout the length of the study. The participating surgeons will have had experience performing at least 100 Whipple procedures to guarantee comparable treatment of patients.

Minimizing measurement bias

The patients will be blinded to the assigned operating technique. Surgeon's blinding will not be possible due to the different techniques used during the operation.

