6.0 ADVERSE EVENT REPORTING

6.1 Adverse Events

Definition: any unfavorable medical occurrence in a human subject including any abnormal sign, symptom, or disease.

Attribution (relatedness), Expectedness, and Seriousness: the definitions for the terms listed that should be used are those provided by the Department of Health and Human Services' Office for Human Research Protections (OHRP). A copy of this guidance can be found on OHRP's website:<http://www.hhs.gov/ohrp/policy/advevtguid.html>

The surgeon will discuss the expected risks of the surgery with the participant and participant and a separate surgical consent for the surgery acknowledging the risks. Expected risks of the surgery are listed below.

- **Perioperative complications:**
iatrogenic injury, convert from laparoscopic approach to open procedure, use of other

hemostatic devices or therapies, blood transfusion

- **Postoperative complications:**

Secondary bleeding/hematoma, delirium, failure to thrive, urinary retention, surgical site infection, urinary tract infection, C-diff, colitis, ileus, delayed gastric emptying, fistula, anemia, pneumonia, intraabdominal abscess, atrial dysrhythmia, myocardial infarction, cellulitis, deep vein thrombosis/pulmonary embolism, anastomotic leakage, re-intervention (operational), blood transfusion, sepsis, death.

The above are complications of the surgical procedure and may be experienced by all patients on whom a Whipple procedure is performed. Surgical complications are routinely identified and documented during the data abstraction process for the American College of Surgeons National Surgical Quality Improvement Program® (NSQIP). NSQIP has very detailed and specific definitions used to assess these postoperative morbidities. For the purposes of this study, the NSQIP definitions for the surgical complications will be utilized.

Surgical complications will not be considered adverse events associated with the study, unless unanticipated and possibly related to the use of the Thunderbeat device. If an adverse event is reported, details related to the event will be obtained from medical record review and direct communication with the PI for severity and relatedness assessment. The adverse event will then be recorded as part of the research and reported as necessary. If it is determined by the PI that the event is anticipated from surgery and not related to the device, it will not be reported as an adverse event as part of this study.

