8.0 DATA AND SAFETY MONITORING

In compliance with the Washington University Institutional Data and Safety Monitoring Plan, the Principal Investigator will provide a Data and Safety Monitoring (DSM) report to the Washington University Quality Assurance and Safety Monitoring Committee (QASMC) and to Olympus, the study sponsor, semi-annually beginning six months after accrual has opened (if at least five patients have been enrolled) or one year after accrual has opened (if fewer than five patients have been enrolled at the six-month mark).

The Principal Investigator will review all patient data at least monthly and provide an annual report to the Quality Assurance and Safety Monitoring (QASM) Committee. This report will include:

- HRPO protocol number, protocol title, Principal Investigator name, data coordinator name, regulatory coordinator name, and statistician

- Date of initial HRPO approval, date of most recent consent HRPO approval/revision, date of HRPO expiration, date of most recent QA audit, study status, and phase of study
- History of study including summary of substantive amendments; summary of accrual suspensions including start/stop dates and reason; and summary of protocol exceptions, error, or breach of confidentiality including start/stop dates and reason
- Study-wide target accrual and study-wide actual accrual
- Protocol activation date
- Average rate of accrual observed in year 1, year 2, and subsequent years
- Expected accrual end date
- Objectives of protocol with supporting data and list the number of participants who have met each objective
- Measures of efficacy
- Early stopping rules with supporting data and list the number of participants who have met the early stopping rules
- Summary of toxicities
- Abstract submissions/publications
- Summary of any recent literature that may affect the safety or ethics of the study

The study principal investigator and Research Patient Coordinator will monitor for serious adverse events on an ongoing basis. Once the principal investigator or Research Patient Coordinator becomes aware of a research related adverse event, the AE will be reported to the HRPO according to institutional guidelines and to Olympus, the study sponsor.

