APPENDIX B: STUDY VISIT SCHEDULE

	Baseline	Intervention	Follow-Up		
	Screening ²	Day of Surgery	Hospital Discharge	30 Day Post-Op Visit ³	90 Day Status ⁵
Past medical history ¹	X				
Informed consent	X				
Physical exam ⁴	X				
Operating time from skin incision to closure (mins)		X			
Anesthesia time (mins)		X			
Intraoperative estimated blood loss (cc)		X			
Administration of blood products		X	X		
Peri and postoperative complications		X	X	X	X
Hospital length of stay			X		
Mortality			X	X	X

¹Study-relevant past medical and surgical history

²Screening procedures to be completed within 60 days of surgery.

³To be performed 30 days from day of surgery \pm 14 days.

⁴Baseline height, weight, gender, karnofsky performance status, medications from pre-surgical physical examination

⁵Medical records (inpatient and outpatient) will be reviewed by a study team member for additional postoperative complications. No direct contact or clinic visit required.

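### The measurement-bias step in 5.2 blinds only the patient, who assesses no listed endpoint, and the plan states no masking for those who abstract and grade complications

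*Combined protocol and SAP*

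**What the plan says.** Section 5.2 has a short paragraph on minimizing measurement bias. It makes two statements: "The patients will be blinded to the assigned operating technique. Surgeon's blinding will not be possible due to the different techniques used during the operation". No other person is described as masked anywhere in the protocol.

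The same section says "Randomization will be performed by a Research Patient Coordinator" and that the assignment "will be documented in the case report file as well as communicated to the treating surgeon".

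Section 7.0 places the operative and post-procedural forms and the 30- and 90-day follow-up forms in RedCap. The operative information is completed from the operative report. Footnote 5 of Appendix B gives the 90-day review of medical records for further complications to an unnamed member of the study team and adds: "No direct contact or clinic visit required".

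Section 6.1 says "Surgical complications are routinely identified and documented during the data abstraction process" for NSQIP, and adopts the NSQIP definitions for this study.

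Section 9.1 lists perioperative complications and postoperative complications to 90 days as secondary endpoints. Section 2.1 names postoperative morbidity beside blood loss in the primary objective. Section 9.4 compares categorical outcomes between arms by chi-square tests and models morbidity both as any grade (1 to 5) and as major grade (3 to 5).

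**The concern.** Measurement bias arises through the people who observe, abstract and grade outcomes. The plan's step against it masks someone who does none of these things. The surgeon cannot be masked, but a later reading of records largely can be, and the plan does not ask for it.

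Several listed complications call for judgement from the chart: gastroparesis, wound infection, pancreatic fistula, anastomotic leakage. So does the grade that separates major from minor morbidity. If the abstractor knows the arm, a small difference in what is counted or how it is graded becomes an apparent device effect, or conceals a harm. The device manufacturer sponsors the trial (6.6, 8.0), so readers will ask how this was guarded against, and the plan as written has no answer.

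**Working it through.** The point rests mainly on setting the sections side by side. The plan gives no figure of its own to reproduce here.

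**1. Does patient blinding protect any listed endpoint?** By source:

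- Blood loss: anesthesia notes and operative nursing staff (5.3).
- Operating and anesthesia times: recorded on the day of surgery (Appendix B).
- Transfusion, complications, mortality: staff and records (9.1, Appendix B).
- Cost: calculated from hospital and 90-day costs (9.1).

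None is reported by the patient, and the 90-day assessment needs no patient contact. Blinding has one small benefit: what a patient reports at the 30-day visit may lead to a complication being recorded.

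**2. Is anything placed between allocation and outcome abstraction?**

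- The arm is in the case report file (5.2).
- Operative and follow-up forms share RedCap, with no access restriction described (7.0).
- The 90-day abstractor is unspecified (Appendix B).
- No section says who assigns the morbidity grades.
- The operative report, which can be expected to describe the technique, is not withheld from anyone.

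No separation is described at any step.

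**3. How much judgement remains?** NSQIP definitions narrow the question of whether an event occurred. The text does not say which scale defines grades 1 to 5. Reference 8 concerns a severity grading system, but no section cites it. Transfusion, re-operation and death leave little room for discretion; the complications named above and the grade leave more.

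**4. What would differential counting do?** This is an illustration on assumed inputs, not an estimate. Assume true any-morbidity of 50% in both arms, 30 patients per arm (9.3), and a fraction u of device-arm patients with morbidity not counted. The observed device rate is p = 0.50 × (1 − u). The control odds are 1, so OR = p/(1 − p). The standard error of log OR is √[1/(30p) + 1/(30(1 − p)) + 1/15 + 1/15], and the 95% interval is OR × exp(±1.96 SE). The last column is the chance of a two-sided P < 0.05 in a comparison of two proportions.

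| u | p | OR | 95% CI | Chance of P < 0.05 |
|---|---|---|---|---|
| 10% | 0.45 | 0.45/0.55 = 0.82 | 0.30 to 2.26 | about 7% |
| 20% | 0.40 | 0.40/0.60 = 0.67 | 0.24 to 1.85 | about 12% |
| 30% | 0.35 | 0.35/0.65 = 0.54 | 0.19 to 1.52 | about 22% |

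The same mechanism can hide harm. With assumed true rates of 60% on device and 50% on control, a 20% undercount on device shows 0.60 × 0.80 = 48% against 50%.

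**The case against.** **The link to unmasked assessors is not stated.** A reader might infer that complications are searched for and graded by people who know the arm. No section says so, and no section says that the abstractor opens the allocation entry. Section 8.0 says "The study principal investigator and Research Patient Coordinator will monitor for serious adverse events on an ongoing basis", which gives the randomizing role a part in safety monitoring. However, 6.1 excludes ordinary surgical complications from study adverse events, so this does not show that the coordinator records the complication endpoints. This objection stands. The supported statement is that nothing prevents unmasked abstraction.

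**Footnote 5 is narrow.** It attaches to the 90-day column and covers additional complications only. The 30-day data follow a routine clinic visit, and treating staff, who may be unblinded, detect the events. Masking the abstractor cannot mask that detection. This also stands and limits what the fix can achieve.

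**NSQIP may already be the safeguard.** Its definitions do reduce discretion. A reader might go further and treat the routine NSQIP record as a masked source that could replace study abstraction. The documents do not show that its abstractors are masked, that it reaches 90 days, or that it covers every trial patient.

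**The stakes are modest.** Under 9.1 these are secondary endpoints, 9.4 calls the analysis descriptive, and even the largest assumed undercount usually gives no significant result. This is fair as to significance. But 9.4 also reports odds ratios with confidence intervals, and a biased estimate matters there whatever its P value.

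**Blood loss is the larger gap.** Theatre staff who can see the technique estimate the primary endpoint (5.3). That is true and is not answered here. It does not make the correctable part any less worth correcting.

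**Conclusion.** The concern holds in a limited form. The plan's measurement-bias step masks nobody who assesses an endpoint, and the plan states no masking or separation for those who abstract and grade complications. That leaves an avoidable route to bias in the morbidity comparisons of 9.4.

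The documents do not establish that such bias would occur, or how large it would be. A reader might take odds ratios of 0.54 to 0.82 as the expected distortion. They follow only from the assumed 50% rate and the assumed one-sided undercounts of 10 to 30%, and their intervals at 30 per arm all include 1. An any-morbidity count also loses a patient only when every qualifying event for that patient is missed.

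Nor does this point bear on the validity of the primary endpoint as 9.1 defines it. It should be corrected because the remedy is cheap.

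**What to change.** In 5.2 and Appendix B, state that:

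- 30- and 90-day complication abstraction and grading is done by a named role in the existing team, other than the coordinator who randomizes;
- that person has no RedCap access to the allocation record or the operative forms;
- that person works from post-operative records, without the operative report;
- the investigator's assessment of device-relatedness for safety reporting remains separate and unblinded.

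The routine NSQIP record may be used as an optional supplementary source, once the team has confirmed who abstracts it, how long it follows patients and which trial patients it covers.

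Cost: a RedCap permission setting and a reallocation of duties. Section 8.0 mentions a data coordinator and a regulatory coordinator as well as the Research Patient Coordinator, so a new post does not appear necessary.

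Downside: masking will be incomplete. Some post-operative notes will reveal the technique, and treating staff who detect events may know it. Complications entered on the day of surgery and at discharge are outside this change, as is the estimate of blood loss. The protocol should acknowledge these limits.

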5.3 Operative Procedure

The surgical procedure will be conducted as planned. The surgeon will follow the subject's assigned group assignment (Thunderbeat™ or conventional) unless determined to be potentially

detrimental to the optimal care of the patient. At that point, all techniques for dissection and hemostasis may be utilized as the surgeon deems necessary.

At least 5 of the procedures will be videotaped for future use to produce educational and training materials. No identifying information will be contained in the video.

The measurement of estimated blood loss (EBL) will come from the intraoperative anesthesia notes where (EBL) is recorded during each surgical procedure in Allscripts and Clindesk. The estimate of operative blood loss is measured by volume in the suction canisters and pads and is historically documented by the operative nursing staff during the operation.

5.4 Postoperative Care

The post operative management is standard of care for all patients who undergo the Whipple procedure and will not be altered by their participation in this study.

5.5 Duration of Follow-Up

Patients will be followed for 90 days following their surgical procedure. Postoperative complications and adverse events will be closely monitored. Patients will be followed until resolution or stabilization of the adverse event. Please see Appendix B for Study Visit Schedule.

5.6 Criteria for Removal from Study

If at any time the constraints of this protocol are considered to be detrimental to the patient's health (e.g. bleeding or other acute health problem) and/or the patient no longer wishes to proceed with the protocol intervention, the patient should be removed from the study and the reason(s) for discontinuation documented in the case report forms.

Otherwise, the patient will receive the intervention and be followed as described.

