3.2 Exclusion Criteria

1. Pregnant or breastfeeding.
2. Surgeon's opinion at the time of dissection that the subject's well being (e.g. bleeding or other independent acute health problems) would be compromised.

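### Section 5.6 directs removal from the study, with bleeding as its first example, and the plan sets no rule for keeping or analysing the data of removed patients

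*Combined protocol and SAP*

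**What the plan says.** Five parts of the protocol bear on a patient for whom the assigned technique becomes unsuitable.

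- **Section 5.6** has two triggers, which apply at any time: the protocol's constraints are considered harmful to the patient, with bleeding named first, or the patient no longer wishes to proceed. In either case "the patient should be removed from the study and the reason(s) for discontinuation documented in the case report forms". The next sentence gives the intervention and the planned follow-up to everyone else.
- **Section 5.3** covers an assignment judged potentially harmful during surgery. From then on "all techniques for dissection and hemostasis may be utilized as the surgeon deems necessary". Removal is not mentioned.
- **Section 3.2(2)** makes a threat to the patient's well-being an exclusion. It rests on the surgeon's "opinion at the time of dissection", and bleeding is again the first example.
- **Section 5.5** is unconditional: "Patients will be followed for 90 days following their surgical procedure".
- **Section 9.1** makes estimated operative blood loss the primary endpoint and counts the need for other hemostatic devices or therapies as a secondary endpoint.

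Section 9.4 names no analysis set. It identifies the Thunderbeat arm by assignment and the comparison arm by the technique that patients had. On timing, Section 5.2 says: "Randomization will only occur after the patient has signed the informed consent". On the surgeon, it says that "blinding will not be possible due to the different techniques used during the operation".

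**The concern.** The first example of a reason for removal is closely tied to the primary outcome. If removed patients are left out of the analysis, membership of the compared groups depends on something that happens after assignment and goes with high blood loss. Randomization then no longer protects the comparison. Removal at different rates in the two arms can create a difference where none exists. Removal of heavy bleeders mainly from the control arm can hide part of a true benefit.

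The sections also give different consequences for what may be the same event: exclusion, a change of technique, or removal. A secondary endpoint that counts the use of other hemostatic devices makes sense only if patients who changed technique stay in the data. Two teams could follow this protocol in good faith and analyse different patients. With 30 per arm, about three patients are enough to matter. A rule chosen after the data are seen would be hard to defend as neutral.

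**Working it through.** **1. What the text settles.**

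| Question | Answer in the documents |
|---|---|
| What follows when the assigned technique is judged harmful during surgery? | 5.3: change of technique. 5.6: removal. 3.2(2): exclusion. No order of precedence is given. |
| Are removed patients followed? | 5.5 sets no condition. 5.6 implies that they are not. |
| Are their data analysed? | Not stated anywhere. |
| Who decides on removal? | 5.6 names nobody. 3.2(2) and 5.3 point to the surgeon, who is unblinded (5.2). |
| Is 3.2(2) judged after randomization? | Not stated. It is inferred, because 5.2 tells the surgeon the assignment and 5.3 has the surgeon follow it. |

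**2. The plan's own sample size.** Section 9.3 gives 60 patients for a 20% difference, alpha 0.05 and power above 80%. It gives no mean, standard deviation or CV, so 60 cannot be reproduced. The largest CV compatible with it can be solved for (two-sided, normal approximation):

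CV = 0.20 / [(1.960 + 0.842) × √(2/30)] = 0.20 / (2.802 × 0.2582) = 0.276

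The t-based value is 0.272. I therefore show CV 0.27 beside a wider assumed range of 0.4 to 0.8.

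**3. Illustration with no true effect.** None of these assumptions is in the documents: lognormal blood loss with mean 1 in both arms, and each patient in the top fifth of one arm removed with probability 0.5 and not analysed. The expected number removed is 30 × 0.2 × 0.5 = 3.

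Let σ² = ln(1 + CV²). The share of total blood loss in the top fifth is S = 1 − Φ(0.8416 − σ). The relative bias in the mean is (1 − 0.5 S)/0.9 − 1.

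| CV | σ | S | Bias |
|---|---|---|---|
| 0.27 | 0.265 | 0.282 | (1 − 0.141)/0.9 − 1 = −4.6% |
| 0.4 | 0.385 | 0.324 | (1 − 0.162)/0.9 − 1 = −6.9% |
| 0.8 | 0.703 | 0.445 | (1 − 0.2225)/0.9 − 1 = −13.6% |

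Simulation with 20,000 trials per setting agrees with these values. Significant results in favour of the arm with removals occur at about 7-9% with Mann-Whitney, the test that Section 9.4 names for non-normal variables, and at about 9-12% with Welch. The nominal rate is 2.5%.

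**4. How far the result depends on the assumptions.**

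- *Weaker selection.* If 3 patients are removed from one arm on an interim signal that correlates 0.5 with log final blood loss, the bias is about −3% at CV 0.27 and −4% to −8% at CV 0.4 to 0.8. In the latter range false wins are about 5% (Mann-Whitney) or 6% (Welch).
- *A common threshold in both arms, no true effect.* The mean bias is about 0 and the two-sided error about 5%.
- *The opposite direction.* With a true 20% reduction and the highest 3 control patients dropped (an extreme case), the observed reduction is 14.1% at CV 0.2765.
- *Removal unrelated to blood loss.* Three per arm lowers power only from 80.0% to 75.7% at CV 0.2765.

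**The case against.** The strongest reply is that Sections 5.3 and 5.6 can be read in sequence: the surgeon first changes technique, and removal is left for cases that this does not resolve. On that reading few patients would be removed for intraoperative bleeding. The reading is fair, but no section states it.

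The data would also usually exist. Blood loss "is recorded during each surgical procedure in Allscripts and Clindesk", complications are routinely abstracted under the surgical quality programme (Section 6.1), and 90-day status is a record review without contact (Appendix B). This stands, and it limits the point to the rule for keeping and analysing data. The assignment wording that Section 9.4 uses for the device arm also leans towards analysis as randomized, although the other half of the sentence does not.

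Section 5.6 covers more than bleeding. Removal before surgery, or because the patient wishes it, need not relate to blood loss.

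Finally, the protocol calls itself a feasibility and quality-improvement registry trial, and Section 9.4 calls its analysis descriptive. That carries less weight, because Section 9.1 sets a comparative primary objective, Section 9.3 claims power for it, and Section 9.4 specifies two-tailed tests at 0.05.

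A reader might go further and infer that recorded data on removed patients will be discarded, that an unblinded surgeon will decide each removal, or that the result will favour the device. The documents support none of these. No section says that data are discarded, Section 5.6 names no decision-maker, and nothing fixes the direction of any bias.

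**Conclusion.** The point holds as a gap in the rules. Section 5.6, with 3.2(2), allows inclusion in the primary comparison to depend on intraoperative bleeding, and no analysis set in Section 9.4 prevents it. Confidence is high about the text and low about the consequence, because the frequency, direction and size of any bias are unknown.

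Under the one-arm illustration the false difference is about −5% at the CV that the sample size implies, and −7% to −14% at CV 0.4 to 0.8. For scale, the planned effect is 20%. False wins are roughly three to five times the nominal 2.5% (7/2.5 = 2.8; 12/2.5 = 4.8). These figures require lognormal blood loss, about three removals confined to one arm, selection on final blood loss, and omission of those patients from the analysis. Milder or balanced removal gives less bias or none.

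Because the frequency of removal is unknown, I rate this as something that should be fixed, not as a demonstrated flaw in the result.

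**What to change.** **Section 9.4.** State that the primary analysis compares all randomized patients by assigned arm and includes every patient whose operation was started. This applies whether or not the assigned technique was kept, the Whipple was completed, or 3.2(2) or 5.6 was invoked after randomization. Tying inclusion to the start of the operation keeps in a patient whose Whipple is abandoned for bleeding. Report by arm the randomized patients whose operation was never started.

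**Section 5.6.** Separate leaving the assigned technique from leaving the study. State that, unless consent to data use is withdrawn, blood loss, complications and 90-day status are still collected and analysed, and report these cases by arm.

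**Sections 3.2(2), 5.3 and 5.6.** State whether 3.2(2) is judged before or after randomization, and reconcile the three sections. Clinical discretion is left as it is.

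**Cost.** A few sentences and no new data collection. The statistical price is some dilution. If 3 of 30 device patients have control-level blood loss (an assumption), the device mean is 0.9 × 0.8 + 0.1 × 1.0 = 0.82 of control, so a true 20% reduction is seen as about 18%. Mann-Whitney power then falls from about 87% to 79% at CV 0.27, and from about 56% to 47% at CV 0.4.
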